**Clinical Trials Protocol for “Reward Processes and Rehearsal in Exposure Therapy”
(NCT06132425)**

Last updated and approved on September 26th, 2023
(IRB#23-000236)

Study Description:

The purpose of this study is to 1) examine the importance of self-reported relief following exposure and 2) test whether positive-focused rehearsal following exposure can improve treatment outcomes for participants who endorse fear of public speaking. Exposure therapy is an extinction-based behavioral technique, often employed in the context of cognitive behavioral therapy. It involves strategically exposing an individual to a feared stimulus in an effort to generate new non-fear associations with that stimulus. Relief refers to the positive, rewarding emotions associated with the absence of an expected aversive outcome following exposure to a feared stimulus. In the current study, participants will engage in a series of short public speaking exposures that take place over two sessions. After every two exposures, participants will be asked to complete either a positive or neutral rehearsal exercise, consisting of recalling either positive or neutral aspects of the speech exposures. At multiple points throughout the study, participants will complete ratings of reward sensitivity, positive affect, relief, and expectancy of the aversive outcome. We will test whether 1) participants with higher reward sensitivity and positive affect will report more relief after each exposure, and 2) participants who report experiencing more relief after each exposure will learn more quickly that the feared stimulus does not predict an aversive outcome (i.e., learning rate). We will also test whether participants who engage in the positive rehearsal exercise will show 1) greater reduction in public speaking anxiety symptoms at the end of the study, 2) greater improvements in reward sensitivity and positive affect, and 3) a faster learning rate and changes in relief over the course of the study. The sample will be volunteer UCLA undergraduates who endorse fear and avoidance of public speaking, measured by two Likert scale screening questions. They will come in at two time points: Visit 1 (first set of exposures) and Visit 2 (second set of exposures), and will complete a few short surveys one week after Visit 2.

Background & Significance:

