Prospective participants will be recruited through the UCLA Psychology Department Subject Pool (i.e., SONA). Prior to signing up for the study, prospective participants recruited through SONA will complete two public speaking anxiety screening questions as part of SONA's prescreening process to determine eligibility for participation. The questions are "How anxious would you feel giving a formal speech before a live audience?" and "How likely would you be to avoid taking a class that required an oral presentation?" Both questions are rated from 0 to 8, with zero indicating no anxiety/never avoid and 8 indicating extreme anxiety/always avoid. Eligible participants must report a score of 6 or higher on the first question and a score of 5 or higher on the second question. Participants will be assigned course credit after participating in the study. Participants will sign up for the study only if they are able to make both visits of the experiment. If the participant does not attend both visits, course credit will still be given for the amount of time the participant spent doing the experiment (i.e., 1 credit for 1 hour).

VISIT 1

On Visit 1, participants will first provide informed consent after the nature of the study has been fully explained and the participant has had time to ask questions. After obtaining informed consent participants will complete a demographics and eligibility questionnaire, which will be reviewed by the researcher upon completion. Ineligible participants (i.e., participants with scores below a 6 on public speaking anxiety and below a 5 on public speaking avoidance, who do not speak English, or are below 18 years of age) will be informed that they do not meet criteria and the research session will be terminated at this time. Participants participating for credit who are found to be ineligible will still receive .5 credits for their time.

Participants will then complete the remaining study questionnaires, the Liebowitz Social Anxiety Scale (LSAS, Leibowitz, 1987), Personal Report of Public Speaking Anxiety (PRPSA, McCroskey, 1970), 8-item version (excluding the suicide item) of the Patient Health Questionnaire-9 (PHQ-9, Kroenke et al., 2001), Positive Valence System Scale (PVSS, Khazanov et al., 2020), Behavioral Activation Scale (BAS, Carver & White, 1994), and a visual analog scale that assesses current positive and negative emotions on a scale from 1-9 (1=neutral/no emotion, 9=extreme emotion; adapted from Lang, 1980).

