After every two exposure trials, participants will then complete a rehearsal exercise (either positive or neutral rehearsal depending on their group assignment). Before the rehearsal exercise, participants will complete the visual analog scale to assess current mood. Participants will then be presented with instructions to complete a verbal rehearsal of the two exposures they just completed, followed by a written rehearsal of the two exposures they just completed. After the rehearsal exercise, participants will again rate their current mood using the visual analog scale, US expectancy ratings ("If you were to complete the same exact speech again, how likely is it that the feared outcome would occur?" where 0 = certain the feared outcome will not occur, 50 = completely uncertain, and 100 = certain the feared outcome will occur; and "Did the feared outcome occur?" where 0 = no, and 1 = yes), and relief ratings ("How relieved are you that the feared outcome did not occur?" where 0 = not at all, 50 = moderately, and 100 = very).

This entire process will be repeated four times, resulting in a total of 8 exposure practices and 4 rehearsal exercises. Participants will then complete a brief set of questionnaires including the LSAS, PRPSA, PVSS, and BAS. The visit is expected to take approximately 60-90 minutes to complete.

FOLLOW-UP

After completion of Visit 2, approximately one week later participants will be sent a short list of questionnaires to be completed independently. Surveys include the public anxiety screening questions, PRPSA, PVSS, and BAS and are expected to take 5-10 minutes to complete.

After completion of the follow-up surveys, participants will be compensated for their time one credit per hour of study participation. All participants will additionally be provided with a referral list at the end of the study.

Statistics & Data Analysis:

Sample size. The sample size will be 74 participants (37 per group). An a priori analysis using G*Power (Faul et al., 2007) indicated that a sample size of 74 would be sufficient to detect a significant effect based on a similar previous study ($d=.30$; Craske et al., 2019) with a power of .80 and an alpha of .05.

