Reward sensitivity and positive affect predicting relief. Linear mixed models will be utilized to assess whether baseline reward sensitivity, measured by the Positive Valence System Scale (PVSS, Khazanov et al., 2020) and the Behavioral Activation Scale (BAS, Carver & White, 1994), and positive affect, measured by a visual analog scale, predict relief rate over the course of exposures. Relief rate will be calculated using a computational model derived from the Rescorla-Wagner model (Rescorla & Wagner, 1972) to capture change in self-reported relief ratings over time. A linear mixed model will also be utilized to assess whether positive affect before an exposure trial predicts subsequent relief on the same trial.

Relief predicting learning rate. A linear mixed model will be utilized to assess whether relief after the first exposure trial predicts learning rate for subsequent exposure trials. Learning rate will be calculated using a computational model derived from the Rescorla-Wagner model (Rescorla & Wagner, 1972) to capture change in self-reported US expectancy ratings over time.

Comparison of positive and neutral rehearsal exercises. A repeated measures between-subjects ANOVA will be utilized to test whether participants in the positive rehearsal intervention show greater reductions in anxiety symptoms (public speaking anxiety screening questions; LSAS, Liebowitz, 1987; PRPSA, McCroskey, 1970) or greater increases in positive affect or reward sensitivity relative to participants in the neutral rehearsal intervention. We will use paired samples t-tests to test whether participants in the positive rehearsal intervention show a faster learning rate or relief rate relative to participants in the neutral rehearsal intervention.

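### Third aim: positive and neutral rehearsal are compared on 8 or 9 outcomes joined by *or*, with no primary outcome, testing order or adjustment, so the efficacy conclusion has no controlled error rate

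*Combined protocol and SAP*

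**What the plan says.** The Specific Aims section lists testing the efficacy of positive rehearsal, relative to neutral rehearsal, as the third of three primary aims. The analysis is in Statistics & Data Analysis, under the comparison of the two rehearsal exercises. A repeated measures ANOVA is to test for "greater reductions in anxiety symptoms (public speaking anxiety screening questions; LSAS, Liebowitz, 1987; PRPSA, McCroskey, 1970"). After the anxiety measures, that sentence goes on to name alternatives: "or greater increases in positive affect or reward sensitivity relative to participants in the neutral rehearsal intervention". Separate t-tests are to examine whether the positive group will "show a faster learning rate or relief rate relative to participants in the neutral rehearsal intervention".

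The same section measures reward sensitivity with two scales, PVSS and BAS. Under Research Design & Methods, prospective participants "will complete two public speaking anxiety screening questions as part of SONA's prescreening process", so the screening measure is two items.

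A significance level appears once, in the sample-size paragraph. It justifies 74 participants for one effect "with a power of .80 and an alpha of .05". Whether tests are one-sided or two-sided is not stated.

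Two other places describe what is expected. The Study Description numbers three expectations, the first being "greater reduction in public speaking anxiety symptoms at the end of the study". The Specific Aims state the hypothesis conjunctively: larger reductions in social phobia symptoms *and* larger gains in reward sensitivity and positive affect, *as well as* faster learning and relief rates. Neither place says which results, or how many, would establish efficacy.

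**The concern.** A plan that tests one efficacy aim on many outcomes needs either a designated primary outcome or a rule for combining the results. Without one, the choice of which result carries the conclusion can be made after the data are seen. The .05 behind the sample size then describes one test, not the conclusion. A report that positive rehearsal works could rest on one chance finding among eight or nine. A reader could not tell it from a result the trial was designed to produce.

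**Working it through.** **1. The plan's own figure.** The sample-size paragraph gives N = 74, d = .30, power .80 and alpha .05. It does not give the test, the number of measurements or the within-person correlation. One set of assumptions reproduces 74: a group-by-time interaction with f = d/2 = .15, m = 3 measurements, correlation .5 and sphericity.

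- λ = f² × N × m / (1 − correlation) = .0225 × 74 × 3 / .5 = 9.99, with 2 and 144 degrees of freedom.
- Power at .05 is .806 at N = 74 and .795 at N = 72.

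On this basis the calculation covers a single test at an unadjusted .05.

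**2. Counting the comparisons.**

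| Outcome group | Tests |
|---|---|
| Screening questions | 1 (2 if tested separately) |
| LSAS, PRPSA | 2 |
| Positive affect | 1 |
| PVSS, BAS | 2 |
| Learning rate, relief rate | 2 |
| **Total** | **8 (9)** |

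This is a minimum. It excludes separate tests at Visit 2 and follow-up, and all tests for the first two aims.

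**3. Family-wise error if tests are independent.** With k tests at .05, the rate is 1 − .95^k.

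- k = 8: 1 − .95^8 = .337
- k = 9: 1 − .95^9 = .370

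**4. Family-wise error if tests are correlated.** The documents give no correlations between outcomes, so a range is assumed. For equicorrelated normal test statistics with correlation ρ and critical value c = 1.96, the rate is one minus the average, over a standard normal z, of [Φ((c − √ρ z)/√(1 − ρ)) − Φ((−c − √ρ z)/√(1 − ρ))]^k. For favourable results only, the second Φ term is dropped, and each test then has a 2.5% chance of a favourable false positive.

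| ρ (assumed) | Any significant difference, k = 8 / 9 | Favourable only, k = 8 / 9 |
|---|---|---|
| 0 | 33.7% / 37.0% | 18.3% / 20.4% |
| .3 | 30.0% / 32.6% | 15.2% / 16.5% |
| .5 | 25.0% / 26.9% | 12.5% / 13.5% |
| .7 | 19.1% / 20.2% | 9.5% / 10.1% |
| .8 | 15.7% / 16.5% | 7.9% / 8.3% |

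The single-test rates for comparison are 5% (any difference) and 2.5% (favourable only). If tests are instead one-sided at .05, the rates are 33.7% / 37.0% at ρ = 0 and 16.8% / 17.7% at ρ = .7, against 5%.

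**5. Smaller families.** Any direction, two-sided .05, ρ = 0 and ρ = .7:

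- Six symptom and reward outcomes: 26.5% and 16.4%.
- Three anxiety outcomes only: 14.3% (1 − .95³) and 10.9%. Favourable only: 7.3% and 5.5%, against 2.5%.

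**6. What adjustment would cost.** On the basis of step 1, Bonferroni over 8 tests (.05/8 = .00625) lowers power per comparison at N = 74 to .53. Over 9 tests (.00556) it is .52. About 116 or 118 participants would be needed for .80. A single primary test avoids that loss.

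**The case against.** A reader might infer that the plan lays down a rule under which any one significant outcome proves efficacy. The documents do not support that. The analysis section lists what will be tested and does not say when efficacy is concluded. The Specific Aims use *and*. If every part had to be significant, there would be no inflation. This part of the objection stands: the defect is an unsettled criterion. It does not remove the concern, because no all-must-succeed rule is written either, and the two sections point different ways.

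A reader might also take 37% as the chance of a false claim that positive rehearsal is better. That needs independent outcomes and one-sided tests at .05, and the plan states neither. With two-sided tests, half of the false positives in each comparison favour neutral rehearsal, and the favourable-only figures apply. The use of .05 for every test is itself an inference from the only level given.

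Learning rate and relief rate may fairly be regarded as mechanism, and the Background presents reward sensitivity and positive affect as the route to better treatment effects. A symptom-only family is therefore a reasonable reading. The error is smaller there but still about twice the nominal rate or more.

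Finally, this is a modest student-sample study. However, it states an efficacy aim, directional hypotheses and an a priori power calculation, and nowhere calls the group comparison exploratory.

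**Conclusion.** The concern holds as an unresolved criterion with a measurable consequence. Third-aim efficacy is to be judged on 8 or 9 comparisons with no primary outcome, order or adjustment, and the hypothesis and the analysis section join the outcomes differently. If each test is run at .05 and any significant result is taken as support, family-wise error under the global null is about 19–37% for assumed correlations from .7 down to 0. It is about 10–20% for favourable results from two-sided tests, against 2.5% for one test. On the three anxiety outcomes alone it is about 11–14% in any direction. The lower ends depend on the assumed correlation and would fall further if it were higher. The count of outcomes comes from the documents.

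**What to change.** Before the data are seen:

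1. **Name one confirmatory test for the third aim at .05, with its sidedness.** A suitable choice is the group-by-time contrast on PRPSA: the group difference in change from Visit 1 to one stated time point, either Visit 2 or follow-up. A group effect averaged over baseline would not test greater reduction. PRPSA matches the public-speaking symptoms in the Study Description and is the only anxiety measure listed at Visit 1, Visit 2 and follow-up. If social phobia symptoms, as in the Specific Aims, are the real target, LSAS could be named instead. It is not listed at follow-up, so the time point would be Visit 2.
2. **Gate the other symptom and reward outcomes.** Test them by Holm only if the primary test is significant, or state that they cannot support an efficacy claim alone. An ungated Holm family at .05 beside a primary test at .05 would bring the error back to about 1 − .95² = 9.8% under independence.
3. **Report learning rate and relief rate as mechanistic results.**
4. **Reconcile the *and* of the Specific Aims with the *or* of the analysis section.**

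The cost is a stricter threshold for secondary outcomes. Neither the data collected nor the sample size needs to change. The power statement should be matched to the contrast chosen. With f = .15 and correlation .5, both assumed, power at N = 74 is .81 for the three-measurement interaction and .72 for a two-measurement one. With correlation .6 the two-measurement figure is .81.

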Participants will complete rehearsal exercises after every two exposures to ensure there is sufficient content for rehearsal. Learning rate (change in expectancy of an aversive outcome across exposure trials) and relief rate (change in relief ratings across exposure trials) will be calculated based on self-reported expectancy and relief ratings provided after each exposure. We hypothesize that regardless of rehearsal group assignment, participants with reduced baseline reward sensitivity and positive affect will exhibit a slower relief rate relative to individuals with elevated baseline reward sensitivity and positive affect, and that lower positive affect will be associated with lower subsequent relief ratings relative to higher positive affect. We hypothesize that regardless of group assignment, higher relief ratings after the first exposure will be associated with a faster learning rate on subsequent exposure trials. Finally, we hypothesize that the positive rehearsal group will lead to significantly greater reductions in symptoms of social phobia and greater increases in reward sensitivity and positive affect at the end of the study, as well as faster learning and relief rates relative to the neutral rehearsal group.

Research Design & Methods:

Visits will either be conducted over HIPAA-compliant video conferencing platform Zoom or in person.

OVERVIEW

The experiment will consist of two study visits. Visit 1 will include informed consent and questionnaires. Participants will then complete a series of short 1-minute public speaking

exposures. After every two exposures, participants will complete a rehearsal task where the participant is asked to use a positive or neutral approach to remember and recount the exposures they have just completed (for a total of approximately 60-90 minutes). Visit 2 will occur approximately 1 week after Visit 1 and will consist of another series of short 1-minute public speaking exposures, followed by the same rehearsal task after every two exposures. Participants will then be asked to complete another series of questionnaires (for a total of approximately 60-90 minutes) For the rehearsal task in Visits 1 and 2, participant will be randomized to practice rehearsing a) focusing on positive emotional aspects of the exposures, or b) focusing on neutral, factual aspects of the exposures. One week after Visit 2, participants will be asked to complete a brief set of questionnaires (approximately 5-10 minutes).

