Participants will be randomized at the start of the study to a positive or neutral rehearsal group. After every two exposure trials, participants will then complete a rehearsal exercise. Before the rehearsal exercise, participants will complete the visual analog scale to assess current mood. Participants will then be presented with instructions to complete a verbal rehearsal of the two exposures they just completed, followed by a written rehearsal of the two exposures they just completed. After the rehearsal exercise, participants will again rate their current mood using the visual analog scale, US expectancy ratings ("If you were to complete the same exact speech again, how likely is it that the feared outcome would occur?" where 0 = certain the feared outcome will not occur, 50 = completely uncertain, and 100 = certain the feared outcome will occur; and "Did the feared outcome occur?" where 0 = no, and 1 = yes), and relief ratings ("How relieved are you that the feared outcome did not occur?" where 0 = not at all, 50 = moderately, and 100 = very).

This entire process will be repeated four times, resulting in a total of 8 exposure practices and 4 rehearsal exercises. The visit is expected to take approximately 60-90 minutes to complete.

VISIT 2

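### Learning rate and relief rate are to be compared between two independently randomised arms with paired-samples t-tests, although no pairs exist

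*Combined protocol and SAP*

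**What the plan says.** Under Statistics & Data Analysis, the paragraph on comparing the positive and neutral rehearsal exercises ends: "We will use paired samples t-tests to test whether participants in the positive rehearsal intervention show a faster learning rate or relief rate", and completes the contrast with "relative to participants in the neutral rehearsal intervention". The sentence before it handles the other outcomes of the same comparison differently: "A repeated measures between-subjects ANOVA will be utilized to test whether participants in the positive rehearsal intervention show greater reductions in anxiety symptoms".

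The design is parallel-group. Under VISIT 1: "Participants will be randomized at the start of the study to a positive or neutral rehearsal group". Under VISIT 2 the exercise is "either positive or neutral rehearsal depending on their group assignment", so nobody changes arm. The planned size is 74 participants, 37 per group. No section describes matching, yoking or crossover.

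The hypothesis in Specific Aims is between groups. It expects the positive arm to do better on symptoms, reward sensitivity and positive affect, "as well as faster learning and relief rates relative to the neutral rehearsal group". The OVERVIEW section allows for incomplete attendance: "If the participant does not attend both visits, course credit will still be given" for the time spent.

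**The concern.** A paired t-test needs a one-to-one link between each value in one arm and a value in the other. This design provides none, so an analyst who follows the sentence has to invent one. There are two ways to do so.

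- **(a) Pair unrelated participants by row.** The p-value then depends on how the file is sorted, and anyone without a partner drops out when completer numbers differ.
- **(b) Pair within participant**, for example Visit 1 with Visit 2. This never compares the arms. It invites the inference that positive rehearsal works better because its within-arm test is significant and the other is not.

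No other arm comparison of the two rates is planned, so the part of the third aim that concerns faster learning and relief rests on this sentence.

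**Working it through.** **Inputs.** From the documents: 37 per group, alpha .05, d = .30. Assumed here: two-sided tests, normally distributed rates with equal SD, one rate per participant, d = .66 as a second effect size (the d that an independent t-test with 37 per arm detects with 80% power), and a 37 versus 31 completer split as an illustration.

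**1. Does the sample size imply a paired design?** The plan gives N = 74 for d = .30 and power .80 without naming the test.
- A paired t-test with dz = .30 needs 90 people two-sided or 71 one-sided.
- An independent t-test needs 176 per arm two-sided.
- A 2-group by 3-time ANOVA interaction gives exactly 74, taking f = .30/2 = .15 and within-person correlation .5 (both assumed): λ = 74 × 3 × .15² / .5 = 9.99, df = 2 and 144, power .806.

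So 74 is not explained by a paired t-test.

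**2. What arbitrary pairing does to the statistic.** With n per arm, both tests have the same numerator, the difference in means. The squared standard errors are:
- independent: (s₁² + s₂²)/n, df = 2n − 2 = 72, critical t = 1.993
- paired: (s₁² + s₂² − 2c)/n, df = n − 1 = 36, critical t = 2.028

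Here c is the sample covariance across rows. With no real pairs, c is noise set by row order. With equal SDs, t(paired) = t(independent)/√(1 − r), where r is the chance correlation, with SD about 1/√36 = .167.

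Take an independent-test p of .047 (t = 2.021). The 95% range of r is about ±1.96 × .167 = ±.327.
- r = +.327: t = 2.021/√.673 = 2.46, p = .019
- r = −.327: t = 2.021/√1.327 = 1.75, p = .088

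Simulation agrees. In ten data sets with the independent p set to .047, the central 95% of 20,000 re-pairings ran from about .019 to .088. The lowest values were .001 to .005 and the highest .115 to .126.

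**3. Operating characteristics of reading (a).** Simulated type I error with 37 per arm is .051 for both tests (100,000 trials). Exact power from the noncentral t has noncentrality d/√(1/n₁ + 1/n₂) for the independent test and d√(m/2) for the paired test, where m is the number of pairs:

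| Completers | d | Independent | Paired |
|---|---|---|---|
| 37 / 37 | .30 | .247 | .241 |
| 37 / 37 | .66 | .800 | .789 |
| 37 / 31 (assumed) | .30 | .229 | .208 |
| 37 / 31 (assumed) | .66 | .761 | .710 |

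In the last two rows pairing discards 37 − 31 = 6 people.

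Two random row orders of the same data disagree on significance in 2.2% of trials at d = 0, 5.6% at d = .30 and 7.6% at d = .50 (40,000 trials each, 37 per arm). Repeat runs gave 2.1 to 2.2%, 5.6 to 5.8% and 7.3 to 7.6%.

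**4. Reading (b).** Suppose both arms truly change by the same amount. With 37 per arm, let p be the power of each within-arm test (36 df, noncentrality dz√37). The chance that positive is significant and neutral is not is p(1 − p), which cannot exceed 25%.

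| dz (assumed) | p | p(1 − p) |
|---|---|---|
| .20 | .220 | 17.1% |
| .30 | .427 | 24.5% |
| .33 | .498 | 25.0% |
| .40 | .658 | 22.5% |
| .50 | .841 | 13.4% |

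A valid between-arm test gives 2.5% in that direction.

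**The case against.** The strongest reply is that this is a one-word slip whose intent is plain. The sentence names both arms, the sentence before it uses a between-subjects ANOVA, and the hypothesis is between groups. Most analysts would run an independent test, and nothing would change. That is likely, but the correction appears nowhere in the document, and this paragraph is the only specification of the comparison. Leaving it means choosing the test after the data are in hand.

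Second, reading (b) fits the sentence poorly, because a within-arm test is not a contrast with the other arm and the plan defines no separate rates per visit. This stands. The percentages in step 4 describe a risk if someone took the word paired at face value, not what the plan says, and they deserve little weight.

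Third, the harm under reading (a) is small, and the loss of participants rests on an assumed split. The passage on missed visits concerns course credit and gives no attrition rate, and participants are asked to sign up only if they can attend both visits. This also stands as a statement about size. It does not supply a pairing rule.

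Finally, the plan does not say that each participant has a single rate. That affects how the correction is worded, not whether it is needed.

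**Conclusion.** The concern holds. The named test does not match the design, and nothing in the document corrects it. This conclusion comes from the text alone and does not depend on the simulations or on reading (b).

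The likely numerical effect is modest. Pairing by row does not inflate type I error and costs about one percentage point of power or less with equal arms. The damage is arbitrariness: orderings disagree in roughly 2% to 8% of trials over d = 0 to .50, and a borderline p of .047 can move between about .019 and .088. Unequal arms would add a loss of participants. The point must be fixed because a stated hypothesis currently has no executable test, not because of a large bias.

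The low power of any independent comparison here (.247 at d = .30 with 37 per arm) is a separate matter.

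**What to change.** In the last sentence of the comparison paragraph, replace the paired-samples t-tests with independent-samples (Welch) t-tests comparing the arms on one learning rate and one relief rate per participant. A linear model with arm as a fixed effect would serve equally well. The definition of the rates can stay as it is. The sentence should say that each participant contributes one value per rate, because the Welch test requires it. If the rates are to be estimated separately by visit, the plan must also say how the two values are combined.

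The cost is one sentence of text, with no new data and no extra analysis work.
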